### Process evaluation:

We will use mixed methods including self-filled questionnaires by participants; programme data to quantify the uptake of each component of the intervention; and the recorded activities by the intervention teams. We will conduct in-depth interviews with participants (n=40; 20 per gender and 10 per arm); and intervention delivery teams; nurses/clinical research assistants (n=6); research assistants (n=5) and peer navigators n= 10; conduct natural group discussions with community group and intervention delivery staff (n=7; 1 with clinic staff, 2 peer navigators groups and 4 community groups [older men, older women and younger men and younger women]). A satisfaction survey will be administered as part of the end-line survey. The process evaluation will explore the following:

- Acceptability / experience.
- Feasibility
- Reach/coverage for whom it worked and didn't work
- Fidelity

## Cost

We will measure the costs in both interventions and control arm, to compare the two arms in their cost in achieving endpoints, i.e., cost per case linked to PrEP (HIV-) and cost per case linked to ART (HIV+). To establish costs, we will use a top-down costing approach using the study budgets and expenditure reports.

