### Cost

What is the cost of the comprehensive SRH component? What is the cost of the peer navigator component? What is the incremental cost per additional person starting and retained in UTT and PrEP at 6 months in each of the arms compared to SoC.

The output of this pilot study will be a costed model of *delivering and evaluating HIV prevention and care through comprehensive SRH for young people (aged <30) living in rural and semi-urban areas of SA*. We anticipate that this will not only inform a large-scale evaluation of the intervention but will provide SA and other southern Africa health policy-makers with evidence for delivering ART-based HIV prevention, which synergize with their planned moves to shift care for long term conditions into the community. This will fill an evidence gap for delivery models to tackle unmet SRH needs, including unplanned pregnancies, STIs and HIV in young people.

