## Study population:

A random sample of N=3000 men and women aged 16-29 years old from the Population Intervention Platform Surveillance Area will be selected, stratified by sex and approached to participate in the study. Based on our recent experience of recruiting for a nested cohort of a similar age range we will expect that ~2000 will still be eligible i.e. alive, still aged 16-29 and residing in the demographic surveillance area. Of these we expect 75% (n=1500) to be contactable and able to provide informed consent; and willing to be traced at one year. Recruitment and outcome ascertainment will be independent of HIV status. Consenting individuals will be randomized in a 2x2 factorial trial to receive one of two delivery models (clinic referral only or peer navigator support), with or without a comprehensive SRH package, with 375 individuals per arm (Figure 2).

Thetha Nami and Isisekelo Sempilo Theory of Change				
The problem	Underlying drivers	Mechanism of action	Activities	Level
Continued high incidence of HIV in adolescents girls and young men and women in rural KwaZulu-Natal, South Africa	
 
External stigma
 
Unemployment & Mobility
 
Adolescent transition
 
Lack of social cohesion
 
Health facilities not suitable for young people
 
	
 
Enabling environment
 
Skills for employability
 
Educational opportunities
 
Positive social norms
 
Social resilience (group efficacy)
 
Support health care delivery
 
	
 
Community youth champions
 
Thetha Nami map social services and educational opportunites
 
Thetha Nami mentoring
 
Thetha Nami- youth groups
 
Thetha Nami-led structured activities
 
Thetha Nami delivery of care and follow-up
 
	Society/ community
	
 
Internalised stigma
 
Common mental disorders
 
Low contraception/condoms
 
Low SRH knowledge (but fertility matters)
 
	
 
HIV status neutral interventions
 
Increase SRH knowledge
 
Address wider health concerns
 
Increase self efficacy
 
	
 
Thetha Nami: Peer Navigators promote mental and sexual health
 
Isisekelo Sempilo: sexual health embedded HIV status neutral care and U=U promotion
 
	Individual

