### Randomisation

A simple random sample (n=2500 eligible men and women aged 16-29) stratified by sex and distributed across the 24 areas will be selected from the demographic surveillance eligibility framework. As explained above and based on our experience of recruiting a sample with a similar age range for our DREAMS impact evaluation we expect to find that 2000 are still eligible, of which 75% are contactable and able to consent. Following informed consent, they will be randomised by sex to one of the four arms.

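### The costing method plans a two-arm comparison of cost per linked case, whereas the stated cost question is the incremental cost per person started and retained at 6 months in each arm against SoC

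*Protocol*

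**What the plan says.** The protocol has two sections headed Cost.

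- **Under Study Outcome**, the section sets the questions. It asks first "What is the cost of the comprehensive SRH component? What is the cost of the peer navigator component", and then for the "incremental cost per additional person starting and retained in UTT and PrEP at 6 months in each of the arms compared to SoC".
- **Under Method, after the process evaluation**, the section gives the analysis. Costs are to be measured for both interventions and for control, "to compare the two arms in their cost in achieving endpoints, i.e., cost per case linked to PrEP (HIV"-negative), with the matching cost per case linked to ART among those who are HIV-positive. On data sources it says "we will use a top-down costing approach using the study budgets and expenditure reports".

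The design is a 2x2 factorial. The Randomisation section says of consenting participants that "they will be randomised by sex to one of the four arms", and the Study population section plans for 375 in each.

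**The concern.** The two Cost sections describe different analyses. The question needs three contrasts with SoC (SRH, peer support, both), each an extra cost divided by an extra effect, where the effect is a person who has started and is still in care or on PrEP at 6 months. The method names one contrast between two unspecified arms, a cost per case with no increment over SoC, and linkage as the effect.

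An analyst could follow only one of them. Following the method would leave the incremental question unanswered, and that question bears most directly on which intervention to carry forward. Average and incremental ratios can point to different arms, and a ratio per person linked need not follow the same pattern as one per person retained.

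**Working it through.** **Side by side**

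| Element | Cost questions (Study Outcome) | Costing method (Method) |
|---|---|---|
| Contrast | each arm v SoC: three contrasts | two arms, not named |
| Ratio | extra cost per extra person | cost per case |
| Effect unit | started and retained | linked to PrEP, linked to ART |
| Time point | 6 months | none given |
| Component costs | SRH and peer, separately | costs measured in both interventions and control |

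The last row is compatible; the first four are not. Nothing elsewhere reconciles them. The Executive Summary says only that the cost of delivery through the different models of care will be established. The Secondary outcomes section does not supply the effect unit either: retention there means 3 of 4 visits over months 1 to 9, and staying on PrEP is assessed at the end of follow-up.

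**Do the measures give different answers?** The protocol states no cost, cost ratio or 6-month retention, so there is no figure to reproduce. The following is an illustration only.

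Inputs from the protocol: 375 per arm; expected uptake of clinical services 10% (SoC), 22% (one intervention) and 38% (both), from the sample size section. These stand in for linkage to PrEP or ART. Inputs assumed, in arbitrary units per participant: SoC 100, SRH 160, peer 140, both 200.

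- Linked per arm: 375 × 0.10 = 37.5; 375 × 0.22 = 82.5 (SRH and peer alike); 375 × 0.38 = 142.5.
- Cost per arm: 37,500; 60,000; 52,500; 75,000.
- Average cost per linked case, C/L: SoC 37,500/37.5 = 1000; SRH 60,000/82.5 = 727; peer 52,500/82.5 = 636; both 75,000/142.5 = 526. The combined arm looks cheapest.
- Incremental cost per extra person linked, (C − C_SoC)/(L − L_SoC): SRH 22,500/45 = 500; peer 15,000/45 = 333; both 37,500/105 = 357. Peer support alone is now cheapest.
- Two-arm incremental contrasts give one figure each. Peer v no peer: 30,000/105 = 286. SRH v no SRH: 45,000/105 = 429. Any intervention v SoC, using mean cost and mean linkage of the three active arms: (62,500 − 37,500)/(102.5 − 37.5) = 385. None of these is one of the three ratios asked for.

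**From linked to retained.** Multiply each arm's linked count by an assumed proportion retained at 6 months.

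| Retained, SoC / active arms (assumed) | SRH v SoC | Peer v SoC | Both v SoC |
|---|---|---|---|
| 80% / 80% | 625 | 417 | 446 |
| 30% / 30% | 1667 | 1111 | 1190 |
| 50% / 30% | 3750 | 2500 | 1563 |

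In the last row, for SRH: 82.5 × 0.30 − 37.5 × 0.50 = 24.75 − 18.75 = 6 extra retained, and 22,500/6 = 3750. With equal retention, the ratios per linked person are simply divided by that retention and the ranking holds. With unequal retention they are not, and here the combined arm becomes cheapest. Cost per linked case therefore does not determine the figure the cost question asks for.

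**The case against.** Several things can fairly be said for the protocol, and they limit the point.

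- **Component costs.** A reader might infer that the method gives no component costs. The text does not support that. Both interventions most naturally means the peer navigators and the SRH package, which the Study process section labels as interventions one and two.
- **Data source.** It is not budgets alone; expenditure reports are named as well.
- **Allocation of shared costs.** It is tempting to fault the absence of a rule for splitting shared clinic and staff costs between arms. Such detail is commonly left to a costing or analysis plan, and the protocol promises a detailed statistical analysis plan. Its absence is no finding.
- **Importance.** Research question 4 asks only what the integrated model costs to deliver, and the declared output is a costed model. The method can serve both. Cost is not among the specific objectives or the numbered primary and secondary outcomes.
- **A fixed multiplier.** A reader might say that cost per linked case understates the true figure by one over retention. It is labelled as what it is, a different quantity. The multiplier also carries over to incremental ratios only if retention is equal across arms: in the 50% / 30% row above, the SRH ratio rises from 500 to 3750, 7.5 times.
- **Loose drafting.** The two arms may mean a factorial margin, and linkage as defined under Participant Survey and Clinic Linkage overlaps with starting treatment. But a margin is still not each arm against SoC, and retention at 6 months is still absent.

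The conflict over contrast, ratio and effect unit survives all of this. It is not a matter of detail deferred to a later plan, because the method section fixes a comparison and an endpoint that differ from those in the question.

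**Conclusion.** The costing method as written does not specify the analysis that would give the three incremental ratios posed under Study Outcome. The documents do not support the stronger conclusion that the trial's cost questions as a whole go unanswered: component costs and the overall cost of delivery may well be obtained.

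No size can be put on the discrepancy. All costs and retention values above are assumptions, and the illustration shows only that the measures can differ and can rank the arms differently. The primary effectiveness outcomes are untouched. The inconsistency is worth correcting because it concerns the protocol's own stated question and can be repaired by wording.

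**What to change.** Amend the Cost section under Method as follows.

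1. Report costs for all four arms, and the incremental cost against SoC for SRH, peer support and the combination.
2. Use started and retained at 6 months as the effect unit and define it from clinic follow-up records, since neither secondary outcome definition supplies it. Say whether PrEP and ART are counted together, as in the question, or separately, as in the method.
3. Keep cost per case linked as a secondary figure.

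If shared costs are to be split by arm, one other section needs attention. Programmatic Data allows programme records, including the navigators' daily reports, to be used only in aggregate by gender, so it should be aligned to permit linked clinic and navigator records to be used by arm. Clinic attenders can already be traced to their arm through the referral vouchers and the linkage system. Navigators serve all young people in their areas, so their work outside the trial has to be separated before their cost is assigned to trial arms.

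The price is an amendment to the text, a few more tables and some added cost-allocation work, mostly on the navigator side.

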### Data Collection Methods

This study employs the following data collection methods:

### (1) Participant Survey and Clinic Linkage

A short survey (described above under enrolment and procedures) will be administered to consenting people participating in the study. The questionnaire will be used to collect data on participant's demographic info and two levels of randomisation identification. The data will be captured on REDCAP on a tablet. The survey will take approximately 5 minutes to complete and will be administered in both English and isiZulu.

The primary outcome of linkage and follow-up by ITT analysis will be measured through identifying the consenting eligible young people who link for PrEP/ prevention counselling or ART initiation. We will use the bar coded referral vouchers as well as other identification within REDCAP to confirm linkage. Using bar coded vouchers and the ClinLink software which is used in all the clinics in the demographic survey area and has been effective to data in linking individuals in the surveillance area when they attend clinic. We will use an algorithm to identify which arm the individual came from, including the bar code on the coupon they bring, their name, age, phone number, id number, area of residence, and the identity of the researcher that recruited them.

The primary outcome of population viral load will be collected from all consenting and contactable participants 12 months after enrolment using the REDCAP survey and Dried Blood Spots as described above. Secondary intervention exposure, sexual health and mental health outcomes will be collected through the same tool.

## (2) Programmatic Data

In addition to the questionnaire, we will collect the programme data records from the clinical tool and the peer navigators daily reporting of their outreach activities and the clinical programme data. We will use the programme data in an aggregate way (disaggregated only by gender) to understand the reach and coverage of the programme and compare that with those who link to care.

### (3) Participant in-depth interviews (IDI) and group discussion

IDIs will be conducted peer navigators (n=10), AHRI nurses/clinical research assistants (n=6) stationed in clinics in the participating communities, trackers (n=5) and a purposive sample of young people aged 16-29 years (n=40; 20 per gender and 10 per arm). The interviews will be conducted by ARHI trained fieldworkers including a senior social scientist in English and isiZulu and will take approximately 60 minutes in length depending on the participant's responses, and this will enable the researchers to understand, contextualize and explore some of the issues around the trial. To limit disturbances and ensure privacy, the IDI will be conducted in a private space suitable for the participant, and audio recorded with interviewees' consents. We will conduct natural group discussions with community group and intervention delivery staff (n=7; 1 with clinic staff, 2 peer navigators groups and 4 community

groups (older men, older women and younger men and younger women). We will ensure representativeness of both sexes in both IDIs and group discussions. The group discussion will contain 6-8 people and will last approximately 120 minutes. Prior to the interview, participants will be encouraged to use pseudo names instead of their real names to ensure anonymity. Also, participants in group discussions will be encouraged to respect individual's opinion and confidentiality where necessary.

#### DATA COLLECTION PLAN

#### Data Collection Team

This study will be managed by the project research team at ARHI. Depending on need, the data collection team will consist of AHRI trained research assistants and trackers; and ARHI trained social science research assistants. Data collectors will be selected based on their experience with both quantitative and qualitative data methods.

### Data Collection Training Requirements

The data collectors will undergo a 2-day training which will include the following content:

- 1. *Protocol training*: this entails the study objectives, the administration of the short survey and IDI guide as well as participant confidentiality and voluntary participation.
- 2. *Redcap training:* This will cover familiarization with survey questions and how it can be captured successfully on Redcap. This will also involve data quality, fidelity and analysis exercise.
- 3. *IDI Data Collection refresher training:* this covers IDI guide content, including training on probing and interview techniques in order to collect quality data. The IDI guide will be available in English and isiZulu, and the training of interviewers will entail a question-by-question discussion exercise as well as relevant terminologies to be used. This process will be led by the Senior Social Scientist.

### Approvals

#### Institutional Ethical Review Board

Ethical approval will be sort from the University of KwaZulu-Natal Biomedical Research Ethics Committee (BREC) and University College London (UCL) ethics board.

See section Ethics and Informed consent

#### DATA MANAGEMENT

#### Electronic Capture of Data and Storage of Electronic Data

Data collectors will administer the short survey using tablets thereby ensuring capturing of real time data. The questionnaire will be loaded onto REDCap and will be accessed for data collection as an application on the tablet. The data management system for these will be based on REDCap (research electronic data capture) developed at Vanderbilt University. The REDCap database resides within a single MySQL database server within a secure server cluster at the Africa Centre. Laboratory data collected for the trial will be output electronically directly from the analyser and imported into the database. Data extractions will be converted to Stata for analysis. Data can be extracted in a variety of formats for analysis. Qualitative data will be stored in the form of Word files or in Excel both of which can be uploaded into Nvivo qualitative data management and analysis programme; the use of MS Word will ensure that data can in future be shared for use in different analysis programmes. These files will be kept on a secure access-controlled folder on a file server at AHRI.

#### Hardcopy Data and Storage

All study-specific data will be stored on a server at AHRI, access to which is strictly controlled. Users are given individually-tailored access only. AHRI has a comprehensive set of SOPs covering the use, validation and security of their computer systems. To avoid loss of data during power fluctuations, servers are installed with stable UPS batteries, with a standby generator in case of power cuts. The server is backed up daily with twice weekly off-site backups. While the study is in progress, study-related forms will be maintained in locked cabinets; access to these cabinets is limited, at study conclusion these documents will be digitized, and the original paper documents destroyed. Digitized document images are indexed and stored indefinitely on the central server. Identifying information will be held by the field team and not kept with the questionnaires. Study-specific electronic laboratory results will be transferred directly from the LIMS. These data will be stored on the AHRI server after transfer. Qualitative data will be managed, stored and archived in consultation with the data manager

#### Audio Data and Storage

The IDI will be tape recorded after prior consent has been obtained from the participant. The audio files will be stored on password protected ARHI PCs and only authorized personnel will have access to them. It is important to mention that audio files will be used for the purpose of this study only. Once the audio files have been transcribed and translated and quality controlled they will be destroyed.

#### Formal information/data security standards

Physical security is maintained through access control for all rooms where data are held. The Institution use industry standard malware and intrusion detection with at least annual penetration tests by a reputable outside security audit company. A software update policy ensures that all operating, data management and malware detection systems are up to date. All servers use a two tier uninterruptable power supplies (UPS). Tier 1 UPS allows switch-over to a local diesel-powered generator, Tier 2 UPS allows for controlled shutdown of all servers if both Tier 1 and generator backups fail. Data on mobile devices are encrypted and unlocked through individual passwords. Communication with the data repository use secure SSL encrypted links. All data will be anonymised. Any personally identifiable information (including names, identity numbers, address, geolocation data, telephone numbers) will

be stored in a separate data enclave in the database with restricted access and identified by separate identifier.

#### Main risks to data security

- i. Physical loss of device/data. Mobile devices can be lost or stolen, this risk is managed by encrypting devices and daily logging individual participant records so that data can be recollected in the case of a device being lost before the data is synchronised. Risk: Low.
- ii. Unauthorised system intrusion and data theft. Intrusion detection systems are in place with annual audit by an external security auditor. Risk: Low

Identity or attribute disclosure risk. Datasets will be assessed for disclosure risk using SDCMicro prior to release on the institutional data repository. Risk: Low

### Data for sharing

Anonymized quantitative data-sets collected in the study will be suitable for sharing. Sharing qualitative transcripts is more challenging. However, we are committed to open access data and so we have developed systems described below to support researchers that may want to use the qualitative data to answer research questions.

**Discovery by potential users of the research data:** The results of the study will be published in a peerreviewed journal. Potential users of the research data will be able to contact the investigators for further information. Furthermore, in accordance with the AHRI Data Sharing Policy, the data will be registered with the AHRI Data Repository. Details of the project and data collected will be available through a URL that will be cited in published papers.

Governance of access: The data custodian at AHRI has the administrative control over granting access to the data to researchers. Anonymized electronic quantitative datasets will be archived and made available to interested external researchers under a data-sharing agreement, after a period of use by the study team. Interested researchers will be required to submit a proposal to use any data for independent analyses. Applicants will be asked to state their analysis objectives, demonstrate they have the capacity to conduct the intended investigations, and to show they understand the local study context to be able to interpret the results appropriately. Qualitative data is more challenging to anonymize. Investigators who are interested in using existing data to answer research questions will be asked to submit letters of intent, with an AHRI named Faculty member as a collaborator. If approved the study would have to undergo relevant IRB and ethical review processes. If analysis is to be undertaken, qualitative data will be stripped of any information that can identify participant before sharing. All data sharing, even those without identifiers, will be through a secure and passwordcontrolled data sharing site, with access strictly limited to transcripts that are relevant to the analysis planned. Requests for data sharing are reviewed by the data custodian and a Data Sharing committee at AHRI. All AHRI staff are bound by the AHRI Data Access Policy, which prohibits any sharing of data with third parties, unless a formal Data Use Agreement has been signed with the third party. For all

analyses, AHRI researchers sign a specific Data Use Agreement that defines the analyses to be undertaken.

The study team's exclusive use of the data: The study team will have exclusive use of the data for 2 years after the study and/or once the primary analysis of the study has been published, whichever comes first. Data may be made available sooner at the discretion of the investigators, where this does not conflict with the publication plans for the study. After the period of exclusive use, data will be made available to potential new users on request.

**Restrictions or delays to sharing, with planned actions to limit such restrictions:** Data sharing will follow the procedures outlined above. All data available for sharing will be anonymized. Consent forms will include a statement to inform study participants that their data may be shared with other users for secondary analyses, with the goal of advancing knowledge

**Regulation of responsibilities of users:** Users will be asked to abide by the AHRI Data Access and Sharing Policy.

